## **4.0 STUDY ENDPOINTS**

### **AIM 1: Establish the safety of an accelerated rTMS protocol for neurocognitive rehabilitation in aMCI.**

Primary Outcomes: Clinically significant structural brain changes; Neurocognitive performance changes; Adverse events

Secondary Outcomes: Psychopathology symptom changes

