### Inclusion Criteria:

- i. Age 60-85
- ii. English as a first/primary language
- iii. Has been diagnosed with MCI by a healthcare provider within the past two years per NIA-AA criteria: (1) Concern regarding cognitive decline reported by patient, informant, or clinician, (2) Objective evidence of impairment for age in 1+ cognitive domains, typically memory, (3) Preserved independent function, (4) no dementia.
- iv. Has met actuarial neuropsychological criteria for aMCI: (1)  $\geq 2$  impaired scores (i.e.  $\leq 16^{\text{th}}$  %ile) within one cognitive domain, or (2)  $\geq 1$  impaired scores (i.e.  $\leq 16^{\text{th}}$  %ile) in  $\geq 3$  cognitive domains, using demographically-corrected normative data. (1) and (2) must include the Memory domain.
- v. The primary suspected etiology of aMCI must be neurodegenerative, with competing differential diagnoses (e.g. psychiatric disorder, movement disorder, reversible causes, substance use) ruled out as the primary etiology/ies following a clinical evaluation by a healthcare provider.
- vi. Ability to provide independent informed consent, consistent with the MCI diagnostic criterion of preserved independent function.

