#### *Eligibility Phone Screening*

Trained study staff will review the eligibility criteria with potential participants. The potential participants' aMCI diagnosis will be verified by Epic chart review (if he/she is an MUSC patient) or by a formal request for medical records initiated by the patient and provided to study staff. PI and neuropsychologist [name] will personally review all potential participants' medical records to ensure that each MCI patient will meet the detailed inclusion/exclusion criteria, which necessitates that the patient has a comprehensive clinical history and neuropsychological test results on file. Should a potential participant not have an established MCI diagnosis, or have incomplete data in support of this diagnosis to the extent that his/her eligibility cannot be readily ascertained, study staff will recommend that he/she complete a clinical evaluation with a clinical neuropsychologist at MUSC or elsewhere, as convenient to him/her.

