## 10.0 STUDY DESIGN AND METHODS

A summary and timeline of all procedures are outlined and described below.

Session Number	Task Description	Location	Approximate Time Commitment
0	Screening Epic and/or medical record review Keel TMS Safety Screen	Telephone	30 minutes
1	Pre-treatment Neurocognitive/Neuropsychiatric Assessment 
Consent/Safety Consent* Keel TMS Safety Screen* TMS Motor Threshold Test Credibility/Expectancy Questionnaire (Pre-treatment)
 
Cognition Montreal Cognitive Assessment (MoCA) NIH Cognition Toolbox NINDS-CSN 30-Minute Neuropsychological Protocol (Hachinski et al., 2006, which includes Semantic and phonemic fluency, Digit Symbol-Coding, Digit Span, Hopkins Verbal Learning Test-Revised, Trail Making Test) WASI-II (Vocabulary, Matrix Reasoning)*
 
Affective Function/Quality of Life Lawton Instrumental Activities of Daily Living Scale (IADL)* Mini-International Neuropsychiatric Interview (M.I.N.I.)* Columbia Suicide Severity Rating Scale (CSSRS) Geriatric Depression Scale (GDS)* Hamilton Depression Rating Scale (HAM-D)* Young Mania Rating Scale (YMRS)* PROMIS Measures: Anxiety, Depression, Applied Cognitive Abilities, Social Participation, General Life Satisfaction, and Fatigue*
	Center for Biomedical Imaging	3 – 3.5 hours
2	Pre-treatment MRI Scans FLAIR, diffusion, T2*/gradient, volumetric scans, resting-state fMRI	Center for Biomedical Imaging	1 – 2 hours
3-5	rTMS Treatment Sessions Review of systems adverse events questionnaire (Yaejee et al., 2015) Momentary Assessment of TMS 8, 3 min sessions rTMS, interspersed with BrainHQ exercises	Center for Biomedical Imaging	2 – 3 hours per day, for 3 days within a 8-day span
6	Post-treatment Neurocognitive/Neuropsychiatric Assessment 
Cognition NIH Cognition Toolbox Montreal Cognitive Assessment (MoCA) NINDS-CSN 30-Minute Neuropsychological Protocol (Hachinski et al., 2006)
 
Affective Function/Quality of Life Lawton Instrumental Activities of Daily Living Scale (IADL)* Mini-International Neuropsychiatric Interview (M.I.N.I.)* Columbia Suicide Severity Rating Scale (CSSRS) Geriatric Depression Scale (GDS)* Hamilton Depression Rating Scale (HAM-D)* Young Mania Rating Scale (YMRS)* PROMIS Measures: Anxiety, Depression, Applied Cognitive Abilities, Social Participation, General Life Satisfaction, and Fatigue*
	Center for Biomedical Imaging	2 - 3 hours

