**Sessions 3-5: rTMS (2 – 3 hours).** A MagVenture MagPro TMS System will be utilized. All participants will receive open-label treatment for approximately eight, 3-minute sessions of intermittent theta burst rTMS on each of three days within an eight-day span. A single session=600 pulses at 120% rMT, iTBS triplets at 50 Hz for 2 s and repeated every 10 s for a total of 190 s to left dlPFC. Total pulses=14,400. To enable adherence and retention, the days do not need to be contiguous. Same day sessions will be separated by 10-15 minutes, but more accounting for participant comfort. After each day of treatment, participants will be asked to complete an rTMS acceptability questionnaire. During treatment breaks participants will complete Momentary Assessment of TMS and 10-15 minutes of Brain HQ exercises between each session and will also have the option of completing tasks at home on intervening days during the treatment schedule. At the end of the final treatment session, participants will be asked to rate the exercises based on difficulty and enjoyment.

**Session 6: In-person Post-treatment Neurocognitive/Neuropsychiatric Assessment (2 - 3 hours).** Within one week following treatment, participants will repeat the pre-treatment neuropsychiatric and neurocognitive assessment for assessment of pre/post treatment changes.

**Session 7: Post-treatment MRI Scans (1 - 2 hours).** Within one week following treatment, participants will repeat the pre-treatment MRI scans for assessment of pre/post treatment changes.

**Session 8: 1 – 3 weeks post-treatment completion.** During the intervening weeks after Sessions 6/7 and before Session 9, the participants will be asked to remotely complete surveys using REDCap. Participants will also be provided with a research account for BrainHQ and asked to engage in at least 20 minutes of brain exercises daily until Session 9.

**Session 9: 4 weeks post-treatment completion.** Participants will again be asked to complete surveys using REDCap. Participants will also be asked to complete the MoCA remotely, as well as acceptability/satisfaction questionnaires regarding the rTMS and BrainHQ interventions.

**Participant Compensation.** Participants will be compensated as follows:

Consent & Session 1:	\$40 for screening and pre-treatment assessments
Session 2:	\$50 for the pre-treatment MRI
Sessions 3 to 5:	\$120 for rTMS treatment (i.e. \$40/day)
Sessions 6 and 7:	\$100 for post-treatment assessments and MRI

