Consent and HIPAA forms will be kept on file for 6 years. Contact information is kept on file for 6 years if the participant consents to allowing their information to remain active in our files, or the contact information is destroyed immediately after the study is completed if participants chose that option on the consent form. Although individual-subject analyses may be written up in publications, the individual subjects producing that data will never be identified by name or initials, or any other identifying information.

*Other protections against risk.* In designing this trial, the research team sought to maximize data collection within the overall priority of maintaining participant comfort and safety. As was discovered in the pilot study by George and colleagues, the proposed design is feasible, does not impose unreasonable expectations of time or effort, or expose patients to risks or limit them from the best available care. In the very unlikely event that a subject endorses transient alcohol or substance abuse during the course of this study, the coordinator will confer with a physician co-investigator prior to proceeding with any treatment.

*Adverse Events & Trial Safety.* Potential conflicts of interest will be reported using the NIH rules for disclosure. Adverse Events (AEs)/Serious Adverse Events (SAEs) occurring during the course of the project will be collected, documented, and reported in accordance with protocol and IRB reporting requirements. All research staff involved with adverse event reporting will receive general and protocol specific AE/SAE training including identification, assessment and evaluation, and documentation and reporting. Any potential adverse events will be identified during the course of the study from participant self-report and administration of the visit assessments and procedures. Research staff will identify adverse events and obtain all available information to assess severity, seriousness, study relatedness, expectedness, outcome and the need for change or discontinuation in the study intervention.

An Adverse Event (AE) is defined as any unwanted change, physically, psychologically or behaviorally, that occurs in a study participant during the course of the trial is an adverse event. A Serious Adverse Event (SAE) is defined as an adverse event that has one of the following outcomes:

- Results in death,
- Is life-threatening,

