Potential worsening of neuropsychiatric symptoms with TMS. Several studies have thus far demonstrated the feasibility of using rTMS in depression without any alarming indicators of exacerbation of symptoms. The research team will work closely with patients to familiarize them with the nature of this experimental setup. All staff will also be trained to be alert to any worsening of neuropsychiatric symptoms and/or psychosocial impairment. Bipolar patients have at times shown hypomanic or manic switches in the course of once-daily rTMS, as such patients with bipolar type I will be excluded. Additionally, all patients will be assessed throughout each day for worsening symptoms. Participants will similarly be queried for worsening suicidal ideation/intent. Drs. [name] or [name] will additionally assess each patient once per week in-person or via telephone during rTMS treatment and the one month study involvement to assess mood, functioning, and safety.

Potential risk of a seizure with TMS. There is a risk that TMS can cause a seizure; but it is rare. The risk of seizure induction is related to the intensity, duration, frequency and rest interval of stimulation. Following the adoption and widespread use of the safety guidelines from a National Institute of Neurological Disorders and Stroke (NINDS) workshop on TMS, only 20 seizures have been reported since 1997, and they usually involved parameters of "higher settings" than the "safe range". To our knowledge, stimulation with the parameters and settings proposed in this study should not cause seizures. Each subject's stimulus intensity is determined by his or her motor threshold and will be carefully calculated before beginning treatment. In this study participants will receive rTMS to the prefrontal cortex, a region far less prone to seizure. Nonetheless, we will watch participants closely for any signs of seizure throughout all procedures. Additionally, our study patients will be free from using known stimulants and medications that are known to increase the risk of seizure (e.g., theophylline).

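### At-home adverse events between contacts depend on recall by memory-impaired participants, with no independent check, so the count could be biased downward by an unknown amount

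*Combined protocol and SAP*

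**What the plan says.** Section 4.0 lists the Aim 1 outcomes: "Primary Outcomes: Clinically significant structural brain changes; Neurocognitive performance changes; Adverse events". The Aim 1 hypothesis in section 1.0 expects no significant adverse events.

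Section 5.0, inclusion criterion iv, gives two actuarial routes to an aMCI classification and ends with the condition "1) and (2) must include the Memory domain". Every participant therefore has objective memory impairment.

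Section 13.0, under Adverse Events & Trial Safety, names two sources of adverse events: "Any potential adverse events will be identified during the course of the study from participant self-report and administration of the visit assessments and procedures".

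The schedule in section 10.0 lists the "Review of systems adverse events questionnaire" at Sessions 3-5, 6 and 8. Session 8 covers weeks 1 to 3 after treatment and is remote: "the participants will be asked to remotely complete surveys using REDCap". The compensation table pays for it weekly over three weeks. The Session 9 row (week 4) has PROMIS measures, the MoCA and two experience questionnaires, but no adverse-event questionnaire.

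Section 15.0 adds two safeguards. On treatment days, "all patients will be assessed throughout each day for worsening symptoms". A study physician also assesses each participant weekly, in person or by telephone, through treatment and the month of study involvement.

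Section 12.0 plans only a descriptive summary of adverse events. The design is single-arm and open-label (sections 2.0 and 3.0).

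**The concern.** For an event at home, such as a fall, an emergency visit or a transient symptom, the follow-up questionnaire and the weekly contact ask the same person to remember it. They repeat one source and do not check it independently. The sample was selected for weakness in exactly that faculty.

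A forgotten event is recorded as no event, which moves the count toward the Aim 1 hypothesis. With no control arm, there is no comparison in which equal under-reporting could cancel. A confidence limit does not help either, because it allows for sampling error and not for events that were never ascertained.

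The protocol's own rules depend on finding such events. Inpatient hospitalisation meets the serious adverse event definition in section 13.0 and is a listed reason for discontinuation in section 14.0. No routine step looks for one that goes unmentioned.

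**Working it through.** **1. Which events depend on recall?** Setting the sections side by side:

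| Setting | How events are found | Depends on later recall? |
|---|---|---|
| Stimulation days (Sessions 3-5) | On-site observation, questionnaire, Momentary Assessment of TMS, same-day symptom monitoring | Little, for events on site |
| Session 6 and 7 visits (within one week) | Questionnaire, psychiatric scales, cognitive tests, MRI review | Partly: tests and MRI do not, the questionnaire does |
| At home, weeks 1-3 | Remote questionnaire plus weekly assessment | Yes |
| At home, week 4 | Weekly assessment; no adverse-event questionnaire listed at Session 9 | Yes |

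The exposed part is events at home between contacts.

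**2. Is there an independent check?**
- *Informant.* The only mention is in inclusion criterion iii, as one possible source of concern about cognitive decline. Informants have no role in adverse-event collection.
- *Records.* Section 8.0 uses Epic for recruitment and eligibility: the "aMCI diagnosis will be verified by Epic chart review (if he/she is an MUSC patient"), or otherwise by a records request. Section 13.0 allows hospital and clinic records to be gathered, but only to complete a serious adverse event report that is already open. That route cannot reveal an event nobody mentioned.

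**3. How large could the effect be?** The plan has no adverse-event rate, threshold or sample-size figure to reproduce. What follows is illustrative.

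Inputs:
- n = 30 target completers or 40 enrolled (section 6.0).
- p = true per-participant risk of an at-home event of a given type. Assumed.
- s = share of such events that is remembered and reported. Assumed; the documents give no value.
- Participants are taken as independent, with one event at most.

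Chance that no event is recorded = (1 − p·s)^n.

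| n | p | s = 1 | s = 0.8 | s = 0.6 |
|---|---|---|---|---|
| 30 | 5% | 0.95^30 = 21% | 0.96^30 = 29% | 0.97^30 = 40% |
| 40 | 5% | 0.95^40 = 13% | 0.96^40 = 20% | 0.97^40 = 30% |
| 40 | 10% | 0.90^40 = 1.5% | 0.92^40 = 3.6% | 0.94^40 = 8.4% |

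If no event of a given type is recorded, the exact one-sided 95% upper limit on the *recorded* rate is 1 − 0.05^(1/n). The limit on the *true* rate is that value divided by s.

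| n | s = 1 | s = 0.9 | s = 0.7 | s = 0.5 |
|---|---|---|---|---|
| 30 | 9.5% | 10.6% | 13.6% | 19.0% |
| 40 | 7.2% | 8.0% | 10.3% | 14.4% |

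These values apply to at-home events only. For events seen on site, s should be close to 1.

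**The case against.** A reader might infer that the whole adverse-event outcome rests on self-report and that the treatment will therefore look safer than it is. The documents do not support that, for four reasons.

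- **Other sources exist.** The ascertainment sentence also names visit assessments and procedures. Seizure, which section 15.0 calls the primary safety concern, is watched for during all procedures. MRI review and objective testing do not depend on remembering events.
- **The weekly assessment matters.** It keeps the recall interval to about a week and is a prompted interview with a physician. It narrows the gap, but it remains an interview of the participant.
- **Poor recall is not shown.** Impairment means scores at or below the 16th percentile, and eligibility requires preserved independence, no dementia and capacity to consent. Nothing in the documents says such people forget a hospitalisation within a week. The recall values above are therefore hypothetical.
- **The net direction for the treatment is not established.** Adverse events are defined as any unwanted change, so unrelated background complaints are counted too, and there is no comparator. Forgetting lowers the recorded count. Whether the overall picture is too favourable cannot be known.

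It is also fair to say that this is a feasibility pilot with a descriptive summary and no zero-event test.

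The narrower gap stands. For at-home events, every scheduled prompt draws on the participant's memory, no independent source is consulted, and week 4 has no adverse-event questionnaire.

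**Conclusion.** The point holds for at-home events between contacts, mainly in weeks 1 to 4 after treatment. Their count, which feeds a primary safety outcome, could be biased downward, and there is no control arm to offset it. The direction rests on forgotten events being recorded as no event. The size is unknown, because the documents give neither a recall rate nor an event rate.

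The calculations show only that moderate under-recall would matter at this sample size. With 30 completers and a 5% true risk, the chance of recording no event rises from 21% to 29% at 80% recall and to 40% at 60% recall. They should not be applied to events during stimulation, and they do not show that the treatment will look safer than it is.

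This is a cheap improvement to ascertainment, not the correction of an error in the plan.

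**What to change.** Add to sections 10.0, 12.0 and 13.0:

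- **Record check.** At Session 9 or at withdrawal, existing staff review the Epic record, or requested outside records, for hospitalisations, emergency visits and new diagnoses since Session 1. They log any event not already reported. This must happen before the name-ID key is deleted, which the Confidentiality paragraph of section 13.0 sets for when data collection is complete. After that, a chart finding could not be linked to the coded data.
- **Questionnaire at Session 9.** Add the existing review-of-systems adverse-event questionnaire to that row.
- **Optional informant.** Let a willing informant answer a separate short adverse-event query. Helping with the participant's own form would give one joint answer, and the sources could not be told apart.
- **Reporting.** Tabulate adverse events by source (participant, visit assessment, informant, record), so that the summary shows how many events the participant's report missed.

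Cost: consent and HIPAA wording, and some minutes of coordinator time per participant. No added visit is needed. Limits: outside charts may be incomplete, and not everyone will have an informant, so the check will be partial. The reported event rate may rise, and the report should say that this reflects fuller ascertainment.

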### Data and Safety Monitoring Procedures.

The PI will choose a group of faculty at MUSC to monitor the data on a bi-annual basis with respect to subject safety issues throughout the award period. The data and safety monitoring plan will include an internal Data Safety Monitoring Committee (DSMC), an external Data and Safety Monitoring Board (DSMB), and the Institutional IRB. The purpose of the DSMC, DSMB, and IRB are to ensure the safety of participants and the validity and integrity of the data.

Data Safety Monitoring Committee (DSMC). The internal DSMC will consist of the PI and co-investigators/consultants on the proposal. The functions of the DSMC will include: 1) providing scientific oversight; 2) reviewing all adverse effects or complications related to the study; 3) monitoring enrollment; 4) reviewing summary reports relating to compliance with protocol requirements; and 5) providing advice on resource allocation. The DSMC will meet quarterly, remotely or in-person. The recommendations of the DSMC will be reviewed and the PI will take appropriate corrective actions as needed.

Data and Safety Monitoring Board (DSMB). A DSMB will be established and will consist of professionals with appropriate expertise, who are willing to participate and who do not have any conflicts of interest. The DSMB will include: 1) two experts in the area of TMS, 2) a biostatistician with expertise in the conduct of clinical trials, and 3) two members with expertise in the treatment of MCI patients. The DSMB will meet on a bi-annual basis. The DSMB will perform the following activities:

- Review the research protocol and plans for data and safety monitoring.
- Evaluate the progress of the intervention, including periodic assessments of data quality and timeliness, participant recruitment, enrollment, and retention, participant risk versus benefit, integrity of the intervention, and other factors that can affect study outcome.
- Consider factors external to the study when interpreting the data, such as scientific or clinical developments that may impact the safety of study participants or the ethics of the study.
- Make recommendations to the internal DSMC and MUSC IRB for continuation or termination of the trial.
- Protect the confidentiality of study data and monitoring.

The DSMB will have the authority to temporarily or permanently discontinue the trial if it perceives that harm is occurring due to the intervention. The DSMB will meet with the internal DSMC yearly to review adverse event reports, patient complaints if any, and enrollment rates. Data will be provided at these meetings by the investigators on key variables that may indicate harm. The DSMB biostatistician will evaluate the confidentiality and integrity of the database and the procedures for recording and storing confidential files. The DSMB will also review the elements of the plan to manage emergencies.

Institutional Review Board (IRB). The MUSC IRB will review and approve the funded protocol; review patient and provider consent forms, ensure protection of patient privacy and safety, and monitor the study on an ongoing basis. Adverse events will be reported to MUSC IRB as they occur. Annual reports to MUSC IRB will indicate enrollment rates, adverse events, new findings that may influence continuation of the study, and reports of the DSMB.

